### **3. Investigational Plan**

#### **3.1 Study Design and Duration**

[figure not shown]
This study is a Phase 1a and 1b, open-label, multicenter, dose escalation and dose expansion study to evaluate the efficacy, safety, tolerability, PK, and PD of cabiralizumab as monotherapy and in combination with nivolumab in patients with selected advanced cancers. Cabiralizumab is a humanized monoclonal antibody directed against CSF1R, and nivolumab is a fully human monoclonal antibody directed against PD-1. For monotherapy arms of the study, cabiralizumab will be given on Day 1 of each 14-day treatment cycle. For the combination arms of the study, cabiralizumab and nivolumab will be given on Day 1 of each 14-day treatment cycle (except for the 3-week dosing regimen cohort). Nivolumab will be administered as an IV infusion over 30 minutes followed by a 30 to 60-minute rest, and then cabiralizumab will be administered as an IV infusion over 30 minutes. If any Grade 3 or higher infusion reaction is observed during the proposed infusion rate of nivolumab 3 mg/kg over 30 minutes, the infusion rate will be extended to 60 minutes for all current and subsequent patients for the duration of this study.

The study will include a Phase 1a dose escalation, Phase 1a 3-week dosing regimen, Phase 1a exploration and a Phase 1b dose expansion. Phase 1a dose escalation consists of 3 cabiralizumab monotherapy cohorts (1aM1, 1aM2 and 1aM3) and 4 cohorts of cabiralizumab in combination with nivolumab (1aC1, 1aC2, 1aC3 and 1aC4). Phase 1a 3-week dosing regimen (1aD) consists of 1 cohort which will administer cabiralizumab in combination with nivolumab every three weeks instead of every two weeks. The Phase 1a exploration is designed to further evaluate the safety, PK, and PD of cabiralizumab as monotherapy and in combination with nivolumab. Phase 1b consists of 7 cohorts (1b1 through 1b7) across 6 cancer types. Patients will be enrolled into either Phase 1a or Phase 1b of the study. The study design is shown in Figure 2.

The study will consist of 3 periods including screening (up to 28 days), treatment, and follow-up.

**Figure 2: FPA008-003 Study Design**

### 3.1.1 Screening Period

All screening evaluations must be completed and reviewed by the Investigator following the procedure noted in the Study Reference Manual for the enrollment process to confirm that patients meet all eligibility criteria before the first infusion of study drug. Written informed consent for participation in the study must be obtained before performing any study specific screening tests or procedures. Screening assessments will be performed within 28 days prior to the first dose of study drug unless otherwise specified.

Study procedure-related AEs that occur after signing of the ICF and before administration of the first study drug dose will be collected during this period.

### 3.1.2 Treatment Period

#### 3.1.2.1 Phase 1a Monotherapy Cohorts and Combination Dose Escalation Cohorts

Phase 1a consists of three cabiralizumab monotherapy cohorts and four dose-escalation cohorts of cabiralizumab in combination with nivolumab with a minimum of 3 patients enrolled in each cohort. The planned dose levels and schedules for the Phase 1a cohorts are as follows:

- Cohort 1aM1: 2 mg/kg cabiralizumab, q2w
- Cohort 1aM2: 6 mg/kg cabiralizumab, q2w
- Cohort 1aM3: 4 mg/kg cabiralizumab, q2w
  - (Dose was de-escalated to 4 mg/kg after DLT observed in 1aM2 (See Section 1.9))
- Cohort 1aC1: 1 mg/kg cabiralizumab + 3 mg/kg nivolumab, q2w
- Cohort 1aC2: 2 mg/kg cabiralizumab + 3 mg/kg nivolumab, q2w
- Cohort 1aC3: 4 mg/kg cabiralizumab + 3 mg/kg nivolumab, q2w
- Cohort 1aC4: 6 mg/kg cabiralizumab + 3 mg/kg nivolumab, q2w

The 2 mg/kg cabiralizumab monotherapy cohort (1aM1) was enrolled first, followed by enrollment in the 1 mg/kg cabiralizumab and nivolumab combination cohort (1aC1). Both cohorts cleared without any DLTs. The 2 mg/kg cabiralizumab and nivolumab combination cohort (1aC2) started after the DLT period cleared in the 1 mg/kg cabiralizumab and nivolumab combination cohort and 2 mg/kg cabiralizumab monotherapy cohort.

The 6 mg/kg cabiralizumab monotherapy cohort (1aM2) opened after the DLT period cleared in the 2 mg/kg cabiralizumab monotherapy cohort (1aM1). There were two DLTs in patients treated in the 1aM2 cohort, both due to laboratory abnormalities. Subsequently, the dose was de-escalated and Cohort 1aM3 (4 mg/kg cabiralizumab monotherapy) was opened. There were two DLTs in the 1aM3 monotherapy cohort and the protocol was subsequently amended to allow higher cutoffs for these laboratory values (see Section 1.8.1). Additional patients were added to the 1aM3 cohort to evaluate the DLT period under the new criteria.

The 4 mg/kg cabiralizumab and nivolumab combination cohort (1aC3) was opened after the DLT period cleared in the 1 mg/kg and 2 mg/kg cabiralizumab and nivolumab combination cohorts and in the respective cabiralizumab monotherapy cohorts.

The 1aM2 cohort was also re-opened with the new DLT criteria. Upon successful completion of the DLT period the 6 mg/kg cabiralizumab and nivolumab combination cohort (1aC4) may be opened.

Depending on the outcome of the cohorts described above, alternative dose cohorts may be opened. All dose escalation decisions will be based on assessment of DLTs, overall safety, and tolerability. Dose escalation decisions will be agreed upon between the Investigators and Sponsor. Prior to initiating each new dose level or expanding an existing dose level, a safety teleconference will be held wherein the Investigators and Sponsor will review patient data, including but not limited to demographics, dosing, concomitant medications, hematology, serum chemistry, and AEs; and confer and document agreement that dose escalation or expanding an existing dose level is considered appropriate. If the Investigators and Sponsor collectively agree, following review of safety, PK, and PD data (if available), that a different dose escalation scheme (e.g., an alternative dose of cabiralizumab monotherapy or in combination with nivolumab) should be used than the one outlined, this will be permitted. Review of safety, PK, and PD profiles may inform decisions to add cohorts with alternative dose levels or dose regimens (e.g., less frequent dosing) in order to reach an optimal target exposure.

Dose escalation will be based on the number of DLTs experienced during the DLT evaluation interval as determined by the Medical Monitor and Investigators (see Section 3.1.2.1.1 for DLT criteria). The DLT evaluation interval begins on the first day of treatment and continues for 28 days. Patients that receive at least 2 doses of study drug during the 28-day evaluation interval or patients who discontinue study treatment for drug-related AEs before receiving 2 doses of study drug will be considered evaluable for DLT determination. In consultation with Investigators, the Sponsor has the option to investigate alternative dose levels to those defined in the protocol.

Dose escalation in Phase 1a will proceed as follows:

- If none of the first 3 evaluable patients in a dose cohort experiences a DLT within the DLT evaluation interval, then the next 3 patients will be treated at the next higher dose cohort.
- If 1 of the first 3 evaluable patients in a cohort experiences a DLT within the DLT evaluation interval, then 3 additional patients will be treated in that dose cohort.
  - If no more than 1 of the first 6 evaluable patients experiences a DLT during the DLT evaluation interval, then the next 3 patients will be enrolled at the next higher dose cohort.
  - If 2 of the first 6 evaluable patients in a cohort experience a DLT, that cohort will be expanded to 9 evaluable patients.

If the MTD is not reached during the Phase 1a combination dose escalation, or subsequent cycles of treatment in cleared Phase 1a combination cohorts provide additional insight on the safety profile, an RD may be selected based on overall tolerability, safety, PK, and PD (if available).

Sponsor has the option to expand any cohort previously established to be safe in order to obtain additional data or to investigate alternative dose levels to those defined in the protocol. Upon completion of the DLT period, up to 40 additional patients may be enrolled in Phase 1aE to fully characterize safety, PK, and PD.

If a patient in Phase 1a monotherapy does not receive 2 doses of study drug and does not complete safety assessments and if a patient in one of the Phase 1a combination cohorts does not receive 2 doses of each study drug and does not complete the safety assessment (e.g., safety lab and/or AE reporting) in the DLT period for reasons other than drug-related AEs (e.g., disease progression or withdrawal of consent), then an additional patient will be enrolled into the cohort so that the cohort has at least 3 patients evaluable for the DLT period. All such discussions and decisions will be documented as part of the dose escalation decision-making process.

Upon completion of the DLT period, Phase 1a patients may participate in an Extended Treatment Period following the guidelines in Section 3.1.2.2.

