## Study Design (Cont.)

### Phase 1a: Dose Escalation

In Phase 1a, a modified 3 + 3 + 3 design will be used to assess the safety of cabiralizumab in monotherapy and in combination with nivolumab.

Dose escalation will be based on the number of DLTs experienced during the DLT evaluation interval as determined by the Investigators and Medical Monitor (see Section 3.1.2.1.1 for DLT criteria). The DLT evaluation interval begins on the first day of treatment and continues for 28 days. Patients who receive at least 2 doses of study drug during the 28-day evaluation interval or patients who discontinue study treatment for drug-related AEs before receiving 2 doses of study drug will be considered evaluable for DLT determination. In consultation with Investigators, the Sponsor has the option to investigate dose levels different than those defined in the protocol.

Dose escalation in Phase 1a proceeds as follows:

- If none of the first 3 evaluable patients in a dose cohort experiences a DLT within the DLT evaluation interval, then the next 3 patients will be treated at the next higher dose cohort.
- If 1 of the first 3 evaluable patients in a cohort experiences a DLT within the DLT evaluation interval, then 3 additional patients will be treated in that dose cohort.
  - If no more than 1 of the first 6 evaluable patients experiences a DLT during the DLT evaluation interval, then the next 3 patients will be enrolled at the next higher dose cohort.
  - If 2 of the first 6 evaluable patients in a cohort experience a DLT, that cohort will be expanded to 9 evaluable patients.
- If 2 of the first 3 evaluable patients experience a DLT within the DLT evaluation interval, then 6 additional patients may be treated in that dose cohort, upon approval of Investigators and the Medical Monitor.
- If the incidence of DLT is > 33% in the overall population up to 9 patients, that dose level has exceeded the MTD and dose escalation will be terminated.

**Study Design  
(cont.)**

Phase 1a: Dose  
Escalation

[REDACTED]	
[REDACTED]	[REDACTED]
[REDACTED]	[REDACTED]
[REDACTED]	[REDACTED]
[REDACTED]	[REDACTED]
[REDACTED]	[REDACTED]
[REDACTED]	[REDACTED]
[REDACTED]	[REDACTED]
[REDACTED]	[REDACTED]
[REDACTED]	[REDACTED]
[REDACTED]	[REDACTED]
[REDACTED]	[REDACTED]
[REDACTED]	[REDACTED]

The study will consist of 3 periods including screening (up to 28 days), treatment, and follow-up.

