The DLT period is defined as the first 28-days (completion of 2 cycles). Upon the first occurrence of a delayed DLT (defined as any DLT that occurs between 4 to 6 weeks after administration of study drug) in any patient enrolled in Phase 1a dose escalation, all ongoing and subsequent DLT periods will be expanded to 42 days for all remaining and subsequent patients enrolled in Phase 1a dose escalation. If no patient experiences a delayed DLT, the DLT period will remain at 28 days for all patients. AST, CK, or LDH laboratory abnormalities without clinical sequelae are not considered a delayed DLT (see Section 3.1.2.1.1).

In the event that no MTD is identified and drug exposure exceeds those deemed necessary based on nonclinical pharmacology data or the clinical PK and PD data (if available), FivePrime and the Investigators may make a decision to discontinue dose escalation.

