#### **3.1.2.1.1 Dose Limiting Toxicity**

A DLT is defined as a study drug-related  $\geq$  Grade 3 AE (using National Cancer Institute [NCI] Common Terminology Criteria for Adverse Events [CTCAE] v 4.03) occurring during the first 28-days, excluding: Grade 3 tumor flare (defined as local pain, irritation, or rash localized at sites of known or suspected tumor), Grade 3 rash, Grade 3 immune-related adverse event (irAE) that resolved to a Grade 1 or less within 14 days, or a transient (resolving within 6 hours of onset) Grade 3 infusion-related AE. Any recurrence of Grade 3 rash, Grade 3 immune-related AE, or Grade 3 infusion-related AE will be considered a DLT. An irAE is defined as a clinically significant AE that is associated with study drug exposure, of unknown etiology, and is consistent with an immune-mediated mechanism.

In the absence of clinical symptoms and other accompanying changes in bilirubin or ALT (as noted in appendices F, G, and H), serum elevations of AST/ALT  $> 12$  xULN and  $\leq 20$  xULN that last for  $< 7$  days will not be considered a DLT and serum elevations of CK and/or LDH  $> 15$  xULN and  $\leq 20$  xULN that last for  $< 7$  days will not be considered a DLT.

Upon the first occurrence of a delayed DLT in any patient enrolled in Phase 1a (defined as any DLT that occurs between 4 to 6 weeks after administration of study drug), all ongoing and subsequent DLT periods will be expanded to 42 days for all remaining and subsequent patients enrolled in Phase 1a dose escalation. If no patient experiences a delayed DLT, the DLT window will remain at 28 days for all patients.

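### If the DLT period is extended to 42 days, the evaluability rule still asks only for 2 doses within 28 days, so a patient lost before Day 42 can be counted as DLT-free

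*Protocol*

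**What the plan says.** **Extension.** The synopsis (Phase 1a: Dose Escalation) and section 3.1.2.1.1 start from a 28-day DLT period. After a first delayed DLT, "all ongoing and subsequent DLT periods will be expanded to 42 days". A delayed DLT is "defined as any DLT that occurs between 4 to 6 weeks after administration of study drug".

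**Evaluability.** Section 3.1.2.1 sets the DLT evaluation interval at 28 days from first treatment. It counts as evaluable "Patients that receive at least 2 doses of study drug during the 28-day evaluation interval", plus patients who stop for a drug-related AE before a second dose. The synopsis has the same rule: "Patients who receive at least 2 doses of study drug during the 28-day evaluation interval". The 0/3, 1/3 and 1/6 decisions count DLTs within that interval.

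**Replacement.** Section 3.1.2.1 adds a patient under a two-part condition: "If a patient in Phase 1a monotherapy does not receive 2 doses of study drug and does not complete safety assessments", for reasons other than a drug-related AE. For combination cohorts the parallel condition is 2 doses of each drug. The stated aim is "so that the cohort has at least 3 patients evaluable for the DLT period".

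**Definition.** Section 3.1.2.1.1 defines a DLT as a drug-related event of Grade 3 or higher "occurring during the first 28-days, excluding" certain events.

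**Decision at stake.** On the re-opened 6 mg/kg monotherapy cohort (1aM2), section 3.1.2.1 says: "Upon successful completion of the DLT period the 6 mg/kg cabiralizumab and nivolumab combination cohort (1aC4) may be opened".

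**The concern.** Days 29-42 are exactly what the extension adds, yet no visible sentence makes a patient's evaluability depend on being observed in them. A patient dosed on Days 1 and 15 who then withdraws consent, is lost to follow-up, or starts new anti-cancer therapy (which ends AE reporting under section 3.4) satisfies the written rule. That patient can be one of the three in a 0/3 decision.

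The underlying cause is that the rule counts doses rather than completed observation. The same patient would count under the 28-day window too, so changing 28 to 42 would not cure it.

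The definition adds a wording conflict. A DLT is limited to the first 28 days, while the trigger for the extension is a DLT at 4 to 6 weeks. Sites could disagree on how to record a Day 35 event.

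Among the listed cohorts this bears mainly on 6 mg/kg: opening 1aC4 after re-opened 1aM2, and then clearing 1aC4. The 6 mg/kg monotherapy cohort has already had two DLTs, both laboratory abnormalities, under earlier cutoffs.

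**Working it through.** The plan states no operating characteristic for the escalation rule, so there is no figure of its own to reproduce.

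**Timing (from the documents).** With 14-day dosing, dose 2 falls on Day 15. A patient is then evaluable with up to 28 − 15 = 13 days of a 28-day window still to run, or 42 − 15 = 27 days of a 42-day window. A patient who only stops treatment after Day 15 is still seen: the first End-of-Treatment visit is 28 (±7) days after the last dose, so 15 + 28 = Day 43, range Days 36-50. AE reporting runs to 100 days after the last dose unless new anti-cancer therapy starts. The gap therefore needs loss of safety observation, not just treatment discontinuation.

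**Replacement rule, literal reading.** The condition is: fewer than 2 doses *and* safety assessments not completed. A two-dose patient fails the first part and is not replaced.

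**Illustration (all rates assumed).**
- p1 = 0.25: DLT risk on Days 1-28.
- p2 = 0.20: risk on Days 29-42 if DLT-free at Day 28.
- m = 0.10 (range 0.05-0.20): share of patients DLT-free at Day 28 who are lost to all safety observation on Days 29-42, independent of late risk.
- Late DLTs that are observed are counted.

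DLT probability per counted patient:
- Full observation: p1 + (1−p1)p2 = 0.25 + 0.75×0.20 = 0.400.
- Current rule: p1 + (1−p1)p2(1−m) = 0.25 + 0.75×0.20×0.90 = 0.385 (0.3925-0.370).
- Evaluability tied to observation: [p1 + (1−p1)(1−m)p2] / [p1 + (1−p1)(1−m)] = 0.385/0.925 = 0.416 (0.408-0.435).

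Probability of clearing a dose with per-patient rate q, using the optional expansion after 2/3:

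C(q) = (1−q)³ + 3q(1−q)²·(1−q)³ + [3q(1−q)²]²·P(Bin(3,q) ≤ k) + 3q²(1−q)·P(Bin(6,q) ≤ k)

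Here k = 1 if 3/9 clears and k = 0 if it does not. The synopsis stops at an incidence above 33%, and 3/9 is 33.3%, so both readings are shown.

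| | q | 3/9 clears | 3/9 fails |
|---|---|---|---|
| Full observation | 0.400 | 0.216 + 0.093 + 0.121 + 0.067 = 0.497 | 0.216 + 0.093 + 0.040 + 0.013 = 0.363 |
| Current rule, m = 0.10 | 0.385 | 0.233 + 0.102 + 0.128 + 0.070 = 0.532 | 0.233 + 0.102 + 0.044 + 0.015 = 0.393 |
| Current rule, m = 0.05 to 0.20 | 0.3925 to 0.370 | 0.515 to 0.567 | 0.378 to 0.425 |
| Tied to observation, m = 0.10 | 0.416 | 0.460 | 0.332 |

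With p2 = 0.10 (true risk 0.325) and 3/9 clearing, the three figures at m = 0.10 are 0.671, 0.688 and 0.630.

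**Share of 0/3 cohorts with an unobserved patient (current rule).** u = (1−p1)m/(1−q) = 0.075/0.615 = 0.122, so 1 − (1−u)³ = 0.32 (0.17-0.56 over the range of m).

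**The case against.** A reader might infer that Day 29-42 events are ignored because the definition says 28 days. The documents do not support that. Section 3.1.2.1.1 itself calls a qualifying event at weeks 4 to 6 a DLT and lengthens the DLT period in response, which would serve no purpose if such events did not count. This is a wording conflict, not a rule that discards late events.

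The replacement rule can also be read more generously. It refers to the DLT period, which becomes 42 days, names withdrawal of consent as a reason, and aims for patients evaluable for that period. Its literal connectives do not work well anyway: the sentence also joins monotherapy and combination patients with *and*. Read loosely, it closes most of the gap. That reading is plausible but not what the text says, and it does not override the separate evaluability sentence.

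The scenario is narrow. The visible text reports no delayed DLT. A drug-related death in the window would itself be a DLT. Patient-level safety review with documented agreement precedes each new dose level (sections 3.1.2.1 and 8) and may catch a lost patient. The escalation table is not visible in either document and could address evaluability. All this limits the size of the point, but the visible counting rule still permits the wrong count.

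Finally, on the illustrative figures the remedy is no closer to full observation than the current rule. At 40% risk with 3/9 clearing, the errors are +0.035 (0.532 − 0.497) for the current rule and −0.037 (0.460 − 0.497) for the remedy. At 32.5% they are +0.017 (0.688 − 0.671) and −0.041 (0.630 − 0.671). That stands. The case for the change is the direction of error in a safety rule, not greater accuracy.

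**Conclusion.** The point holds as a minor one. Once the DLT period is extended, the visible counting interval and evaluability rule remain at 28 days and require doses rather than observation. The literal replacement rule leaves a two-dose, then-lost patient in the count as DLT-free. The dose-counting weakness is present at 28 days too.

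The size cannot be derived from the documents. Under the assumed 40% risk and 10% loss, the clearing probability rises by about 0.03 (0.50 to 0.53, or 0.36 to 0.39 if 3/9 fails). This depends on the assumed rates, on loss being unrelated to late risk, and on how 3/9 is read. A reader might infer that anyone stopping treatment early goes unobserved, or that a too-toxic dose is likely to be cleared because of this gap. The End-of-Treatment visit, 100-day AE reporting and small increments do not support either inference.

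**What to change.** 1. **Synopsis and 3.1.2.1, evaluability.** Define the DLT evaluation interval as the applicable DLT period (28 days, or 42 once extended). Count a patient as evaluable only if they (a) have a DLT in that period, (b) discontinue for a drug-related AE before receiving 2 doses, as now, or (c) receive at least 2 doses of each assigned drug and complete safety assessments, including safety labs, to the end of that period.
2. **3.1.2.1, replacement.** Change *and* to *or* between the missed-dose and incomplete-assessment conditions, so that any other patient is replaced.
3. **3.1.2.1.1, definition.** Replace the 28-day limit with the applicable DLT period. Define a delayed DLT as an event meeting the DLT criteria except for timing, with onset on Days 29-42, and keep the synopsis exemption for AST, CK and LDH abnormalities without clinical sequelae.

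**Cost.** Mostly wording. For a patient who stops after Day 15, the nominal Day 43 End-of-Treatment visit can supply the closing labs; a visit on Days 36-41 would need later labs as well. Under the assumptions above, an extended window needs 3/0.925 = 3.24 enrolled per 3 evaluable, or 0.24 extra (0.12-0.53), and 9/0.925 = 9.73 per 9, or 0.73 extra (0.35-1.59). Replacements within a 28-day window would add to this and are not quantified. Because only DLT-free patients are replaced, the counted DLT rate is slightly high (0.416 against a true 0.400), which leans toward caution.

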#### **3.1.2.1.1 Dose Limiting Toxicity**

A DLT is defined as a study drug-related  $\geq$  Grade 3 AE (using National Cancer Institute [NCI] Common Terminology Criteria for Adverse Events [CTCAE] v 4.03) occurring during the first 28-days, excluding: Grade 3 tumor flare (defined as local pain, irritation, or rash localized at sites of known or suspected tumor), Grade 3 rash, Grade 3 immune-related adverse event (irAE) that resolved to a Grade 1 or less within 14 days, or a transient (resolving within 6 hours of onset) Grade 3 infusion-related AE. Any recurrence of Grade 3 rash, Grade 3 immune-related AE, or Grade 3 infusion-related AE will be considered a DLT. An irAE is defined as a clinically significant AE that is associated with study drug exposure, of unknown etiology, and is consistent with an immune-mediated mechanism.

In the absence of clinical symptoms and other accompanying changes in bilirubin or ALT (as noted in appendices F, G, and H), serum elevations of AST/ALT  $> 12$  xULN and  $\leq 20$  xULN that last for  $< 7$  days will not be considered a DLT and serum elevations of CK and/or LDH  $> 15$  xULN and  $\leq 20$  xULN that last for  $< 7$  days will not be considered a DLT.

Upon the first occurrence of a delayed DLT in any patient enrolled in Phase 1a (defined as any DLT that occurs between 4 to 6 weeks after administration of study drug), all ongoing and subsequent DLT periods will be expanded to 42 days for all remaining and subsequent patients enrolled in Phase 1a dose escalation. If no patient experiences a delayed DLT, the DLT window will remain at 28 days for all patients.

